10.3 Response Duration (RECIST 1.1 and iRECIST)

Response duration will be measured from the time measurement criteria for CR/PR or iCR/iPR (whichever is first recorded) are first met until the first date that recurrent or progressive disease is objectively documented, taking as reference the smallest measurements recorded on study (including baseline).

10.4 Stable Disease Duration

Stable disease duration will be measured from the time of start of treatment until the criteria for progression are met, taking as reference the smallest sum on study (including baseline).

10.5 Methods of Measurement

The same method of assessment and the same technique should be used to characterize each identified and reported lesion at baseline and during follow-up. Assessments should be identified on a calendar schedule and should not be affected by delays in therapy. While on study, all lesions recorded at baseline should have their actual measurements recorded at each subsequent evaluation, even when very small (e.g. 2 mm). If it is the opinion of the radiologist that the lesion has likely disappeared, the measurement should be recorded as 0 mm. If the lesion is believed to be present and is faintly seen but too small to measure, a default value of 5 mm should be assigned. For lesions which fragment/split add together the longest diameters of the fragmented portions; for lesions which coalesce, measure the maximal longest diameter for the “merged lesion”.

- 10.5.1 **Clinical Lesions**. Clinical lesions will only be considered measurable when they are superficial and ≥ 10 mm as assessed using calipers (e.g. skin nodules). For the case of skin lesions, documentation by colour photography including a ruler to estimate the size of the lesion is recommended. If feasible, imaging is preferred.
- 10.5.2 **Chest X-ray**. Chest CT is preferred over chest X-ray, particularly when progression is an important endpoint, since CT is more sensitive than X-ray, particularly in identifying new lesions. However, lesions ≥ 20 mm on chest X-ray may be considered measurable if they are clearly defined and surrounded by aerated lung.
- 10.5.3 **CT, MRI**. For this protocol the baseline CT scans within the first 12 weeks must conform to the requirements outlined in Appendix VII. For assessment of response using RECIST 1.1, CT is the best currently available and reproducible method to measure lesions selected for response assessment. This guideline has defined measurability of lesions on CT scan based on the assumption that CT slice thickness is 5 mm or less. Other specialized imaging or other techniques may also be appropriate for individual case [ref RECIST 1.1]. For example, while PET scans are not considered adequate to measure lesions, PET-CT scans may be used providing that the CT conforms to Appendix VII.
- 10.5.4 **Ultrasound**. Ultrasound is not useful in assessment of lesion size and should not be used as a method of measurement. If new lesions are identified by ultrasound in the course of the study, confirmation by CT is advised.
- 10.5.5 **Endoscopy, Laparoscopy**. The utilization of these techniques for objective tumour evaluation is not advised. However, they can be useful to confirm complete pathological response when biopsies are obtained or to determine relapse in trials where recurrence following complete response or surgical resection is an endpoint.
- 10.5.6 **Tumour Markers**. Tumour markers alone cannot be used to assess objective tumour response. If markers are initially above the upper normal limit, however, they must normalize for a patient to be considered in complete response.
- 10.5.7 **Cytology, Histology**. These techniques can be used to differentiate between PR and CR in rare cases if required by protocol (for example, residual lesions in tumour types such as germ cell tumours, where known residual benign tumours can remain). When effusions are known to be a potential adverse effect of treatment (e.g. with certain taxane compounds or angiogenesis inhibitors), the cytological confirmation of the neoplastic origin of any effusion that appears or worsens during treatment when the measurable tumour has met criteria for response or stable disease is advised to differentiate between response or stable disease and progressive disease.

10.6 **Time to Tumour Progression**

Time to tumour progression will be measured from date of registration until documented progression or death.

10.7 **Overall Survival**

Overall survival will be calculated from date of registration until death.

10.8 **Censoring**

Patients alive without progression at end of study will be censored at last visit/known to be alive and progression free.

11.0 SERIOUS ADVERSE EVENT REPORTING

The descriptions and grading scales found in the NCI Common Terminology Criteria for Adverse Events (CTCAE) will be utilized for Adverse Event (AE) reporting (version can be found in Appendix V). All appropriate treatment areas should have access to a copy of the CTCAE. A copy of the CTCAE can be downloaded from the CTEP web site:

http://ctep.cancer.gov/protocolDevelopment/electronic_applications/ctc.htm.

All serious adverse events (SAE) defined as per ICH guidelines (see below) and other adverse events must be recorded on case report forms. In addition, all “reportable” serious adverse events are subject to expedited reporting using the CCTG SAE form. The term ‘reportable SAE’ is used in the definitions which follow to describe those SAEs which are subject to expedited reporting to CCTG.

11.1 Definition of a Reportable Serious Adverse Event

- All serious adverse events, regardless of whether they are unexpected or related to protocol treatment, occurring during the treatment period and within 30 days after the last protocol treatment administration, must be reported in an expedited manner. Any late deaths related to protocol treatment or other serious adverse event occurring after this 30-day period which is unexpected and related to protocol treatment must also be reported in an expedited manner (see Section 11.2 for reporting instructions).
- Known drug related events are excluded from expedited reporting unless they cause hospitalization, death or are life threatening
- SAE’s that are considered definitely related to disease are excluded from expedited reporting but must be reported as adverse events
- A serious adverse event (SAE) is any adverse event that at any dose:
 - results in death
 - is life-threatening
 - requires inpatient hospitalization or prolongation of existing hospitalization (excluding hospital admissions for study drug administration, transfusional support, scheduled elective surgery and admissions for palliative or terminal care)
 - results in persistent or significant disability or incapacity
 - is a congenital anomaly/birth defect

Medical and scientific judgement should be exercised in deciding whether expedited reporting is appropriate in other situations such as important medical events that may not be immediately life-threatening or result in death or hospitalization but may jeopardize the patient or may require intervention to prevent one of the events listed above.

11.2 Serious Adverse Event Reporting Instructions

All reportable serious adverse events must be reported using a web-based Electronic Data Capture (EDC) system being used for this trial. For details about accessing the EDC system and completing the on-line SAE report form, please refer to the CCTG Generic Data Management Guidebook for EDC Studies posted on the IND.225 section of the CCTG website (www.ctg.queensu.ca).

Within 24 hours: Complete preliminary Serious Adverse Event Report and submit to CCTG via EDC system.

Within 7 days: Update Serious Adverse Event Report as much as possible and submit report to CCTG via EDC system.

EDC SAE web application interruption:

In the rare event that internet connectivity to the EDC SAE system is disrupted, please print and complete a paper copy of the SAE Report, available from the trial specific website.

FAX paper SAE Report to:

[name], Study Coordinator
Canadian Cancer Trials Group
[contact]

Please use the same timelines for submission as for direct EDC reporting.

Once internet connectivity is restored, the information that was FAXED to CCTG on the paper SAE Report must also be entered by the site into the EDC SAE web application.

Local internet interruption:

If you are unable to access the EDC SAE system, and cannot access a paper copy of the SAE Report from the trial website, please phone the IND. 225 trial team [contact]) to obtain a copy of the SAE Report by FAX. Once completed, the report must be FAXED back to CCTG as indicated above. Once internet connectivity is restored, the information that was FAXED to CCTG on the paper SAE Report must also be entered by the site into the EDC SAE web application.

In cases of prolonged internet interruptions, please contact the CCTG Safety Desk for further instructions [contact]).

11.3 Other Protocol Reportable Events – Pregnancy Reporting

11.3.1 Pregnancy Prevention

Women of Childbearing Potential (WOCBP) and males who are enrolled in the trial must have agreed to use contraceptive method(s) as described in Eligibility Criterion 5.1.7. Investigators may wish to additionally advise the female partners of male participants about pregnancy prevention guidelines when appropriate and compliant with local policy.

11.3.2 Pregnancy Reporting

The investigator is required to report to CCTG any pregnancy occurring in female participants, and female partners of male participants. Pregnancies occurring up to 4 months after the completion of study treatment must also be reported.

The investigator should report the pregnancy in a timely manner, within 24 hours of learning of the pregnancy using the CCTG Pregnancy Reporting Form available from the trial webpage.

Once informed consent has been obtained, the form should be updated to provide further pregnancy information and to reflect the outcome of the pregnancy. All follow-up reports must be submitted to CCTG in a timely manner. For pregnant partner of trial participant (and pregnant participants, if required by local policy), a copy of the signed signature page of the pregnancy follow-up consent must be submitted to CCTG.

Documents outlined above (including updates) must be sent to the CCTG safety desk [contact]/ [contact]).

If the pregnancy results in death (e.g. spontaneous abortion, stillbirth); is life-threatening; requires inpatient hospitalization or prolongation of existing hospitalization; results in persistent or significant disability/incapacity; is a congenital anomaly/birth defect, then an SAE report must be additionally submitted as described above. Please note, hospitalization for labour/delivery alone does not constitute an 'inpatient hospitalization' for the purposes of pregnancy reporting.

11.4 CCTG Responsibility for Reporting Serious Adverse Events to Health Canada

The CCTG will provide expedited reports of SAEs to Health Canada (Office of Clinical Trials) for those events which meet regulatory requirements for expedited reporting, i.e. events which are BOTH serious AND unexpected, AND which are thought to be related to protocol treatment (or for which a causal relationship with protocol treatment cannot be ruled out).

11.5 CCTG Reporting Responsibility to Merck

Merck will be notified of all protocol reportable serious adverse events (as defined in Section 11.1), via CIOMS report within 2 working days of receipt of report at CCTG. CCTG, as sponsor, will determine regulatory reportability in Canada.

11.6 Merck Reporting Responsibilities

Merck will report all regulatory reportable serious adverse events from non-CCTG trials (Safety Updates) with pembrolizumab to CCTG within the timelines outlined in the contract. CCTG will review these events to determine which meet the criteria (serious, unexpected, drug related) for reporting to IND.225 investigators. Merck will report these events to Health Canada.

11.7 Reporting Safety Reports to Investigators

CCTG will notify Investigators of all Safety Reports (Serious Adverse Events (SAEs) from this trial and Safety Updates (SUs) from other clinical trials) that are reportable to regulatory authorities in Canada as reported to the CCTG. This includes all serious events that are unexpected and related (i.e. possibly, probably, or definitely) to protocol treatment. The reports will be posted to the CCTG trial IND.225 web-based safety monitoring utility.

Investigators must notify their Research Ethics Boards (REBs) of events which involve corrective action(s) to be taken as a result of the event(s) such as protocol and/or informed consent changes. The date of REB Submission for these SAEs and SUs will need to be entered into the CCTG trial IND.225 web based safety monitoring utility and documentation of REB submission must be retained in the study binder on site. The REB submission template provided by CCTG can be used to assist with tracking, submission, filing and monitoring.

The submission of events to your ethics board should be done as soon as possible (we suggest within 30 days). REB submissions greater than 90 days from the date of notification will be regarded as delinquent and a major deficiency will be assigned. These safety reports are to be filed in the trial files on site.

12.0 PROTOCOL TREATMENT DISCONTINUATION AND THERAPY AFTER STOPPING

12.1 Criteria for Discontinuing Protocol Treatment

Patients may stop protocol treatment in the following instances:

- Intercurrent illness which would, in the judgement of the investigator, affect assessments of clinical status to a significant degree, and require discontinuation of protocol therapy.
- Unacceptable toxicity as defined in Section 8.0.
- Tumour progression or disease recurrence as defined in Section 10.0.
- Request by the patient.
- Completion of therapy as outlined in Section 8.0. Efforts should be made to maintain the investigations schedule and continue follow-up, even if patients discontinue protocol treatment prematurely and/or no longer attend the participating institution.

12.2 Duration of Protocol Treatment

Maximum 1 year or until one or more criteria in Section 12.1 are met. After 1 year, patients may continue on pembrolizumab but will transition to standard of care management.

12.3 Therapy After Protocol Treatment is Stopped

At the discretion of the investigator.

12.4 Follow-up Off Protocol Treatment

See Section 9.2.

13.0 CENTRAL REVIEW PROCEDURES

13.1 Central Radiology Review

At the conclusion of the trial, a central review of x-rays and/or scans will be carried out for response. CT scans will be reviewed and analyzed for texture analysis. For purposes of reporting, the results of both local and central radiology reviews will be included.

13.2 Central Pathology Review

There will be no central pathology review for this study.

14.0 STATISTICAL CONSIDERATIONS

14.1 Objectives and Design

This is an open-label, multicentre, phase II trial of pembrolizumab in first line therapy of metastatic melanoma. The primary objective is to assess whether tumour texture parameters from a CT scan correlates with response in metastatic melanoma patients treated with pembrolizumab. Secondary end points include duration of response, overall response rate and survival.

14.2 Sample Size and Duration of Study

This is the first trial to evaluate tumour texture parameters to correlate them with tumour response to pembrolizumab.

Without knowing the true fraction of patients with CT features that are considered “positive” or “negative” it is not possible to do a true power calculation and the trial should be viewed as exploratory assessment of the potential of texture parameters to correlate with response. However, assuming the response rate to pembrolizumab is 35%, then a sample size of 80 patients will allow analysis of CT texture analysis parameters among 20-25 responding patients versus 55-60 non-responding patients. We propose to recruit 84 patients to identify 80 evaluable patients to assess for texture parameters in responders and non-responders which may support further evaluation in definitive trials. Sensitivity, specificity, positive and negative predictive values will be assessed.

Accrual rate is anticipated to be approximately 5-10 patients/month for total duration of accrual of 6-12 months.

Patients will be followed on study for the duration as indicated in Section 12.

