2.0 BACKGROUND INFORMATION AND RATIONALE

Metastatic melanoma historically has had a very poor survival. Thankfully this is now changing due to advent of new targeted drugs and breakthroughs in immunotherapy. Programmed cell death 1 (PD-1) receptor is an inhibitory receptor expressed by T cells. Its ligand, PD-L1 is frequently expressed within the tumour microenvironment including tumour cells. Tumour models have shown that PD-1 negatively regulates the effector phase of T-cell responses after ligation of PD-L1 expressed within the tumour [Blank 2004]. Several drugs have been developed that block PD-1 and hence augment the T cell response. The most mature results have been obtained in advanced melanoma patients and indicate high response rates, high quality responses and prolonged duration of response and prolonged survival.

Pembrolizumab is a highly selective, humanized monoclonal IgG4-kappa isotype antibody against PD-1 that is designed to block the negative immune regulatory signalling of the PD-1 receptor expressed by T cells [Hamid 2013]. Pembrolizumab has shown improved response rates, response duration and survival compared to standard treatments for melanoma [Ribas 2015; Patnaik 2014]. Patients receiving pembrolizumab had an overall RR of 38% with durable responses and approximately a further 30% of patients with disease control. The 1 year survival in this trial was 67% and 50% at 2 years in patients with metastatic melanoma [Daud 2015]. Pembrolizumab was also compared to ipilimumab in first line therapy for metastatic melanoma and showed a better RR and OS rate compared to ipilimumab with a RR of 34% compared to 12% and OS at 12 months of 74% compared to 58% for ipilimumab [Robert 2015]. In this study and subsequent phase III studies, pembrolizumab is administered intravenously at 2 mg/kg every 2 weeks for a total of 2 years. Recent results from pharmacokinetic studies indicate that a flat dose of 200 mg IV is sufficient for exposure and that there is no additional advantage to weight-based dosing. In addition, responses occur early within the first 8 weeks and it is possible that 2 years of consecutive therapy may not be needed given the durable responses seen with ipilimumab short courses.

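### Two planning figures in Section 14.2 do not follow from their inputs: 35% of 80 is 28 versus 52, not 20-25 versus 55-60, and 84 patients at 5-10 per month take 8.4-16.8 months, not 6-12.

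*Combined protocol and SAP*

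**What the plan says.** Section 14.2 (Sample Size and Duration of Study) declines to give a formal power calculation. Because the fraction of patients with positive or negative CT features is unknown, it says "it is not possible to do a true power calculation and the trial should be viewed as exploratory assessment". In its place it offers a conditional statement. The premise is "assuming the response rate to pembrolizumab is 35" per cent, and the conclusion is that "a sample size of 80 patients will allow analysis of CT texture analysis parameters among 20-25 responding patients versus 55-60 non-responding patients". A small allowance for non-evaluable patients follows: "We propose to recruit 84 patients to identify 80 evaluable patients". Sensitivity, specificity and predictive values are to be assessed.

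The same section gives the timeline: "Accrual rate is anticipated to be approximately 5-10 patients/month for total duration of accrual of 6-12 months".

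Section 2.0 (Background) cites two response rates for pembrolizumab in melanoma: "Patients receiving pembrolizumab had an overall RR of 38% with durable responses" and, in the first-line comparison with ipilimumab, "a RR of 34% compared to 12" per cent. The assumed 35% lies between them.

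**The concern.** Each statement gives its inputs and its result together, so each can be checked by one multiplication or division, and each fails.

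The responder split matters more. With no power calculation, it is the only number Section 14.2 offers to show what 80 patients can deliver. Responders are the denominator for sensitivity and non-responders the denominator for specificity. As written, a reader cannot tell whether the design rests on a response rate of 35% or on one of 25-31%.

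The accrual window matters for planning sites, drug supply and the analysis date. It affects no estimate.

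**Working it through.** **Inputs.** From Section 14.2: response rate 35%; 80 evaluable patients; 84 recruited; 5-10 patients per month; stated results 20-25 versus 55-60 and 6-12 months. From Section 2.0: response rates of 34% and 38%.

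**(a) Responder split.** Expected responders = N x p.

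- Stated inputs: 0.35 x 80 = 28 responders and 80 - 28 = 52 non-responders. The nearest ends of the stated ranges, 25 and 55, each miss by 3 patients.
- Rate implied by the stated counts: 20/80 = 25% to 25/80 = 31.25%.

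Attempts to recover the stated range:

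- *Loss of evaluable patients.* The 80 are already the evaluable patients, and 20 + 60 and 25 + 55 both equal 80, so nobody is missing from the split.
- *The recruited number.* 0.35 x 84 = 29.4 responders, further away.
- *The cited rates.* 0.34 x 80 = 27.2 and 0.38 x 80 = 30.4. Neither lies in 20-25.
- *Another N at 35%.* The stated responders need 20/0.35 = 57 to 25/0.35 = 71 patients; the stated non-responders need 55/0.65 = 85 to 60/0.65 = 92. The two ranges do not overlap, so no single N gives both.
- *A sampling range.* For a binomial count with N = 80 and p = 0.35, the 2.5th to 97.5th percentiles are 20-36. P(20 to 25) = 0.261, P(more than 25) = 0.718 and P(fewer than 20) = 0.021. The stated range covers only the lower part of what 35% would produce.

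Effect on precision: largest 95% half-width (true value 50%, normal approximation) = 1.96 x sqrt(0.25/n).

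| Quantity | At 35% of 80 | At the stated split |
|---|---|---|
| Sensitivity (n = responders) | n = 28: 18.5 points | n = 25 to 20: 19.6 to 21.9 points |
| Specificity (n = non-responders) | n = 52: 13.6 points | n = 55 to 60: 13.2 to 12.7 points |

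**(b) Accrual.** Duration = N / monthly rate.

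- 84/10 = 8.4 months and 84/5 = 16.8 months. With 80 patients instead of 84: 8.0 to 16.0 months.
- Rate needed for the stated window: 84/12 = 7 to 84/6 = 14 per month.
- At 7-10 per month, 84 patients accrue in 12.0 to 8.4 months, inside the stated maximum. Below 7 per month the plan overruns, by at most 16.8 - 12 = 4.8 months. Six months would need 14 per month, above the fastest stated rate.
- The stated window fits 60 patients exactly at both ends (60/10 = 6; 60/5 = 12). The documents mention no target of 60, so this is only something for the sponsor to check.

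**The case against.** The best defence is that very little depends on these numbers. The trial is declared exploratory, with no alpha, power, threshold or stopping rule for either figure to disturb. Section 14.2 does not derive 80 from the split; it describes what 80 would yield, so correcting the split leaves the case for 80 as it was. The error understates the scarcer group, so it is cautious for sensitivity, and it flatters specificity by less than one point (13.6 against 12.7-13.2). A count of 20-25 responders is also quite possible at 35%. On accrual, the text is hedged as anticipated and approximate, and the stated and recomputed windows overlap from 8.4 to 12 months.

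All of this stands as a limit on weight, and it is why the point is a correction and not a challenge to the design. It does not reconcile the numbers. Being exploratory excuses the lack of a power calculation, not a wrong product in the sentence that stands in for one. No discount from 35% is stated that would make 20-25 a deliberately cautious range. The hedge on accrual cannot cover a lower end that no stated rate reaches, or an upper end exceeded by 40% (4.8/12) at the slowest stated rate.

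One caution is also fair: the half-widths assume a fixed rule for calling a scan positive. If the cut-off is chosen from the same data, simple binomial intervals may understate the uncertainty.

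**Conclusion.** Both figures are wrong as written. The split consistent with 35% of 80 is 28 versus 52, and accrual of 84 patients at 5-10 per month takes 8.4-16.8 months. The impact is low: the sample size is unchanged, no decision depends on either figure, and the largest half-width moves by about 1 to 3 points for sensitivity (better) and by less than 1 point for specificity (worse). Accrual overruns only below 7 patients per month, by up to 4.8 months.

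The split result takes the 35% rate and 80 evaluable patients at face value. The accrual result takes a constant monthly rate within the stated range; the documents give no ramp-up period, and a slow start would lengthen accrual. The documents do not show how either discrepancy arose.

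**What to change.** In Section 14.2:

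- Restate the split as about 28 responding and 52 non-responding patients. If 20-25 responders is what the sponsor intends, state and justify an assumed rate of 25-31% instead, which would be below both rates cited in Section 2.0.
- Restate accrual as about 8-17 months at 5-10 patients per month. If 6-12 months is intended, state a rate of 7-14 per month and the basis for it; the documents offer none at present.
- Check whether the 6-12 month window was worked out for a different number of patients.
- Optionally, add the largest 95% half-widths at 28 and 52 patients (about 19 points for sensitivity, 14 for specificity), noting that they assume a cut-off fixed in advance.

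The cost is wording only, with no extra patients. The one drawback is a longer stated accrual period.
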